15.8 Physical Examination

Physical examination (including neurologic examinations) will be listed using the safety population and include the following information:

- Date
- Neurological examination:
 - Mental Status (Normal/Abnormal)
 - o Cranial Nerves (Normal/Abnormal)
 - Motor System (Normal/Abnormal)
 - Muscle Strength (Normal/Abnormal)
 - o Gait, stance and coordination (Normal/Abnormal)
 - Sensation (Normal/Abnormal)
 - Reflexes (Normal/Abnormal)
 - Autonomic Nervous System (Normal/Abnormal)
- Mini-Mental State Examination (MMSE):
 - o Result (Normal/Abnormal)
 - Score

- International Cooperative Ataxia Rating Scale (ICARS):
 - Postural and Gait Disturbance
 - Limb Ataxia
 - o Dysarthria
 - Oculomotor disorders
 - Total score

The results will be summarized by dose group and using the safety population, displaying counts and percentages for abnormal results and summary statistics for scores (considered as continuous, see Section 9.2 for details).

16 Analyses of Other Endpoints

16.1 Pharmacokinetics

16.1.1 Analysis of PK Concentrations

All individual pharmacokinetic (PK) plasma concentrations of M8891 will be listed by time point using the safety population. Subjects that are not included in the PK analysis set will be flagged, and the list will be sorted so that they are at the bottom of the list.

The listing for the plasma concentration of M8891 will include the following:

- Scheduled and actual date/time
- Concentration
- Time relative to scheduled time (HH:MM:SS)

The PK plasma concentrations will also be summarized descriptively using the PK Analysis Set by dose and time point using the PK analysis set. Values below the lower limit of quantification (LLOQ) will be taken as zero for descriptive statistics of concentrations.

Individual plasma concentration-time profiles (linear and semi-logarithmic scale) will be plotted using the safety population. Subjects that are not part of the PK analysis set will be flagged in the plot.

Mean plasma concentrations per dose group and day will be plotted using scheduled time points on the linear (± Sd) and semi-logarithmic scale. If mean minus Sd is negative, Sd will be truncated at 0. In case PK blood samples were not performed within the time window specified in the protocol, these calculations and plots will be repeated excluding the respective plasma concentrations. The PK analysis set will be used for these figures.

The following tables and figures will be provided:

Tables

- Individual Plasma Concentrations of M8891 and Descriptive Statistics by Scheduled Time for Each Dose Group after Single Dosing (Cycle 1 Day 1)
- Individual Plasma Concentrations of M8891 and Descriptive Statistics by Scheduled Time for Each Dose Group after Multiple Dosing (Cycle 1 Day 15)
- Individual Trough Plasma Concentrations of M8891 and Descriptive Statistics by Scheduled Time and Dose Group

Figures

- Individual M8891 Plasma Concentration-Time Profiles by Dose Group and Day, Linear Scale
- Individual M8891 Plasma Concentration-Time Profiles by Dose Group and Day, Semi-Logarithmic Scale
- Mean (±Sd) M8891 Plasma Concentration-Time Profiles by Dose Group and Day, Linear Scale
- Mean M8891 Plasma Concentration-Time Profiles by Dose Group and Day, Semi-Logarithmic Scale
- Individual M8891 Plasma Concentration-Time Profiles for Single and Multiple Dose Overlaid, Linear Scale. (Overlaid means that the x-axis is hours post dosing on the same day.)
- Individual M8891 Plasma Concentration-Time Profiles for Single and Multiple Dose Overlaid, Semi-Logarithmic Scale
- Mean (±Sd) M8891 Plasma Concentration-Time Profiles by Dose Group, for Single and Multiple Dose Overlaid, Linear Scale
- Mean M8891 Plasma Concentration-Time Profiles by Dose Group, for Single and Multiple Dose Overlaid, Semi-Logarithmic Scale

Results of the PK urine sampling will be listed using the safety population, including the following information:

- Time of last urination before start of dosing (HH:MM)
- Collection start and end date/time
- Volume collected
- Any comment recorded in the CRF
- Concentration of M8891
- Total amount of M8891 (calculated as volume x concentration)

Subjects that are not included in the PK analysis set will be flagged, and the list will be sorted so that they are at the bottom of the list. The urine PK values (volume, concentration and amount) will also be summarized by dose group and study day for the scheduled measurements using the PK analysis set.

Volume and amount will be added for multiple voidings and concentration will be calculated used an average weighted by volume.

16.1.2 Estimation of Individual PK Parameters

Pharmacokinetic parameters will be calculated by the PK/CCI Merck, Darmstadt, Germany, using standard non-compartmental methods and the actual administered dose. PK parameters will be calculated using the actual elapsed time since dosing, given with a precision of 14 significant digits or the SAS format Best12. In cases where the actual sampling time is missing, calculations will be performed using the scheduled time and flagged in listings. For AUC₀₋₂₄, if the actual sampling time at 24 hours is not equal to the scheduled observation time, AUC₀₋₂₄ will be calculated based on estimated concentration at the scheduled time and not the concentration at the actual observation time.

The following plasma PK parameters of M8891 will be calculated, when reliable on Day 1 and Day 15:

C _{max}	Maximum observed concentration
C _{max} /Dose	The Dose normalized maximum observed concentration. Normalized using the actual dose, and the formula $C_{\text{max}}/\text{Dose}$.
t _{max}	The time to reach the maximum observed concentration collected during a dosing interval (unless otherwise defined, take the 1 st occurrence in case of multiple/identical C _{max} values)
AUC _{0-t}	The area under the concentration-time curve (AUC) from time zero (= dosing time) to the last sampling time (t_{last}) at which the concentration is at or above the lower limit of quantification. Calculated using the mixed log linear trapezoidal rule (linear up, log down).
AUC _{0-t} /Dose	The Dose normalized AUC from time zero to the last sampling time (t_{last}) at which the concentration is at or above the lower limit of quantification. Normalized using the actual dose, and the formula $AUC_{0-t}/Dose$.
AUC _{0-∞}	The AUC from time zero (dosing time) extrapolated to infinity, based on the predicted value for the concentration at t_{last} , as estimated using the linear regression from λ_z determination. AUC _{0-∞} =AUC _{0-t} +C _{last pred} / λ_z

AUC _{0-∞} /Dose	The Dose normalized AUC from time zero extrapolated to infinity. Normalised using actual dose, using the formula AUC _{0-∞} /Dose.
AUCτ	The area under the concentration-time curve (AUC) over the dosing interval from T_1 =0 h to T_2 = τ h. Calculated using the mixed log linear trapezoidal rule (linear up, log down). For single dose, AUC τ is calculated as a partial area with the defined time range. In multiple dose profiles AUC τ is calculated at steady state from one pre-dose time point to the dosing interval time. In cases where the actual observation time is not equal to the scheduled observation time AUC τ will be calculated based on the estimated concentration at τ hours, and not the concentration at the actual observation time.
AUC _τ /Dose	The Dose normalized AUC over the interval from T_1 =0 h to T_2 = τ h. Normalized using actual dose, using the formula $AUC_{\tau}/Dose$.
AUCextra%	The AUC from time t_{last} extrapolated to infinity given as percentage of $AUC_{0-\infty}$. $AUC_{extra\%} = (extrapolated area/AUC_{0-\infty})*100 = (1 - [AUC_{0-t}/AUC_{0-\infty}])*100$.
λ_z	Terminal first order (elimination) rate constant. Determined from the terminal slope of the log-transformed concentration curve using linear regression on terminal data points of the curve
t _{1/2}	Apparent terminal half-life. $t_{1/2} = \ln (2)/\lambda_z$
CL/f	The apparent total body clearance of drug following extravascular administration, taking into account the fraction of dose absorbed. $CL/f = Dose_{p.o.}/AUC_{0-\infty}$.
CL _{SS/f}	The apparent total body clearance of drug at steady state following extravascular administration, taking into account the fraction of dose absorbed. $CL_{SS/f} = Dose_{p.o.} / AUC_{\tau}$
CLR	The renal clearance of drug. $CL_R = Ae_{0-\infty}/AUC_{0-\infty}$ or Ae_{0-t}/AUC_{0-t}
$V_{\mathrm{Z/f}}$	The apparent volume of distribution during the terminal phase following extravascular administration, based on the fraction of dose absorbed. $V_{z/f} = Dose/(AUC_{0-\infty}*\lambda_z)$ following single dose. $V_{z/f} = Dose/(AUC_{\tau}*\lambda_z)$ following multiple dose.
Racc(AUC)	The accumulation factor to assess the increase in exposure until steady state is reached. $R_{acc(AUC)}=(AUC_{\tau} \text{ after multiple dose (at steady state)}) / (AUC_{0-\infty} \text{ after single dose})$

R _{acc(Cmax)}	The accumulation factor to assess the increase in maximum concentration until steady state is reached. $R_{acc(Cmax)} = (C_{max} \text{ after multiple dose (at steady)})$
	steady state is reached. $R_{acc(Cmax)} - (C_{max} \text{ after multiple dose (at steady state)})/(C_{max} \text{ after single dose}) = C_{max} D_{15}/C_{max} D_{1}$

The following urine PK parameters of M8891 will be calculated, when reliable, for the QD and BID dosing, on Day 1 and Day 15:

Ae_{τ}	The cumulative amount excreted during a complete dose interval at steady state. Amount_Recovered = Σ (Concentration * Volume) from T_1 to T_2 , where T_1 and T_2 denote the start and end time of the dose interval at steady state respectively.
Aeτ%	The cumulative percentage of dose excreted during a complete dose interval at steady state. Percent_Recovered = 100*Amount_Recovered/Dose.
Ae _{0-t}	The cumulative amount excreted from time zero (= dosing time) to the end of the current collection interval after dosing. Amount_Recovered = Σ (Concentration * Volume)
Ae _{0-t} %	The cumulative percentage of dose excreted from time zero (= dosing time) to the end of the current collection interval after dosing. Percent_Recovered = 100*Amount_Recovered/Dose
Ae _{0-∞}	The cumulative amount excreted from time zero (dosing time) to infinity. $ Ae_{0-\infty} = Ae_{0-t} + ((Ae_{0-(t-1)} - Ae_{0-t})/(t_{last-1} - t_{last}))/\lambda_z \text{ where } \lambda_z \text{ is the excretion rate or } Ae_{0-\infty} = (Ae_{0-t} / AUC_{0-t}) * AUC_{0-\infty} $
Ae _{0-∞} %	The cumulative percentage of the dose that is excreted from time zero (= dosing time) to infinity. Percent_Recovered = 100*Amount_Recovered/Dose

The following PK parameters will be calculated for diagnostic purposes and listed, but will not be summarized:

- The time interval (h) of the log-linear regression ($\lambda_{z \text{ low}}$, $\lambda_{z \text{ upp}}$) to determine λ_{z} .
- Number of data points (N_{λ}) included in the log-linear regression analysis to determine λ_z .
- Goodness of fit statistic (Rsq) for calculation of λ_z .

The regression analysis should contain data from at least 3 different time points in the terminal phase consistent with the assessment of a straight line on the log-transformed scale. Phoenix WinNonlin best fit methodology will be used as standard. The last quantifiable concentration

should always be included in the regression analysis, while the concentration at t_{max} and any concentrations <LLOQ which occur after the last quantifiable data point should not be used. AUC_{extra}% should be less than 20%. If AUC_{extra}% is greater than 20%, all parameters derived using λ_z (i.e. λ_z , $t_{1/2}$, AUC_{0-\infty} AUC_{extra}%, V_z, CL) will be included in the parameter outputs and descriptive statistics but will be flagged and discussed appropriately. Any flags should be included in the study specific SDTM.

The coefficient of correlation (R^2) should be ≥ 0.8 and the observation period over which the regression line is estimated should be at least twofold the resulting $t_{1/2}$ itself. If these criteria are not met, then the rate constants and all derived parameters (e.g.CL, and Vz etc.) will be included in the parameter outputs and descriptive statistics but will be flagged and discussed appropriately. Any flags should be included in the study specific SDTM.

Partial areas AUC_{τ} should be calculated using the scheduled dosing interval, as defined in the CTP. The actual dosing interval calculated from CRF time data should not be used. The following rules apply when calculating the partial area AUC_{τ} within the observed time interval from T1 to T2:

- If the start time of the interval (T₁) occurs before the first observation, the observation at T₁ will be estimated using the linear interpolant between the first datapoint and C0. For single dose data C0= 0 when the drug was administered via an extravascular route or via infusion, and C0 is the estimated dosing time intercept when the drug was administered as an IV bolus. For steady state models, C0 is the minimum concentration value occurring within the time interval T₁ to T₂.
- If either T₁ or T₂ falls within the time range in which samples were taken, but does not coincide with an observed data point, then a linear or logarithmic interpolation is performed to estimate the corresponding concentration value. Whether a linear or logarithmic interpolation is used will depend on the method of AUC calculation e.g. linear up log down.
- If the end time of the interval (T_2) occurs after the last measurable concentration and the terminal regression (λ_z) is estimable, then λ_z is used to estimate the concentration at time T_2 . The log trapezoidal rule will be used to calculate the area from the last observation time to the end time of the partial area (T_2) . If λ_z cannot be estimated the partial area will not be calculated.

Concentrations below the lower limit of quantification (<LLOQ), which are before the last quantifiable data point, will be taken as zero for calculating the AUC. Unless otherwise specified in the CTP, pre-dose samples that occur before the first drug administration will be assigned a time of 0 hours, as if the sample had been taken simultaneously with the study drug administration. The same applies to the very first pre-dose sample of a multiple dose study.

Dose dependent parameters (e.g. CL, Vz) will not be calculated for metabolites.

The Phoenix WinNonlin NCA Core Output will be provided in a separate listing.

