16.1.3 Analysis of PK Parameters

All PK parameters will be listed using the safety population. Subjects that are not included in the PK analysis set will be flagged, and the list will be sorted so that they are at the bottom of the list.

The PK parameters will also be summarized descriptively per day by dose group using the PK analysis set.

The following tables and figures will be provided:

Tables

Individual Pharmacokinetic Parameters of M8891 in Plasma and Descriptive Statistics by Treatment after Single Dosing (Cycle 1 Day 1)

Individual Pharmacokinetic Parameters of M8891 in Plasma and Descriptive Statistics by Treatment after Multiple Dosing (Cycle 1 Day 15)

Individual Accumulation Ratios of AUC, Ae and Cmax in Plasma and Descriptive Statistics by Treatment

Individual Dose Normalized Pharmacokinetic Parameters of M8891 in Plasma and Descriptive Statistics after Single Dosing (Cycle 1 Day 1)

Individual Dose Normalized Pharmacokinetic Parameters of M8891 in Plasma and Descriptive Statistics after Multiple Dosing (Cycle 1 Day 15)

Figures

Scatter Plots: M8891 Dose-normalized PK Parameter (eg, AUC0-t, AUC0-∞ and Cmax) versus Treatment, Single Dose (with linear regression)

Box Plots: M8891 Dose-normalized PK Parameter (eg, AUC0-t, AUC0-∞-, and Cmax) versus Treatment, Single Dose

Scatter Plots: M8891 Dose-normalized PK Parameter (eg, AUC, and Cmax) versus Treatment, Multiple Dose (with linear regression)

Box Plots: M8891 Dose-normalized PK Parameter (eg, AUC, and Cmax) versus dose

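### SAP 16.1.2 does not limit AUC0-inf and CL/f = Dose/AUC0-inf to single dose; taken on Day 15 as written, CL/f would understate clearance by the factor AUCtau/AUC0-inf

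*SAP*

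**What the plan says.** SAP 16.1.2 governs its whole plasma parameter list with one sentence: "The following plasma PK parameters of M8891 will be calculated, when reliable on Day 1 and Day 15". Four rows of the list matter here.

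- AUC0-inf: "The AUC from time zero (dosing time) extrapolated to infinity, based on the predicted value for the concentration at" the last sampling time. It is computed as AUC0-t plus predicted Clast/λz.
- AUC0-inf/Dose, the same area divided by the actual dose.
- AUCextra%, the share of AUC0-inf that lies beyond the last sample.
- CL/f: "The apparent total body clearance of drug following extravascular administration, taking into account the fraction of dose absorbed", computed as Dose/AUC0-inf.

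None of these rows names a day or a single dose. Other rows in the list do make the distinction:

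- CLss/f: "The apparent total body clearance of drug at steady state following extravascular administration, taking into account the fraction of dose absorbed", computed as Dose/AUCtau.
- Vz/f, which has one formula after a single dose (with AUC0-inf) and another after multiple dosing (with AUCtau).
- Racc(AUC): "The accumulation factor to assess the increase in exposure until steady state is reached", which divides steady-state AUCtau by the single-dose AUC0-inf.

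SAP 16.1.3 lists all PK parameters and summarises them per day. One planned table is "Individual Pharmacokinetic Parameters of M8891 in Plasma and Descriptive Statistics by Treatment after Multiple Dosing (Cycle 1 Day 15"; neither it nor its dose-normalised counterpart names the parameters it will hold.

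**The concern.** Dose divided by AUC0-inf estimates apparent clearance only when the area comes from that one dose. On Day 15 the subject has taken 14 earlier daily doses. The curve carried to infinity includes what remains of them, so the denominator is too large and the result too low.

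If the text is followed literally, the Day 15 table would hold two clearances for the same subject on the same day, CL/f and CLss/f, that differ only by formula. Day 15 AUC0-inf/Dose would be too high by the reciprocal factor. CL/F and CLss/F are both named among the secondary PK endpoints (Protocol 8.3.1.2; SAP Section 5), so a reader of the report would have reason to look at both.

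**Working it through.** **Inputs from the documents**

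- Dosing interval: 24 h, once daily (Protocol 5.1.3.1).
- Last Day 15 profile sample: 24 h post-dose, taken on Day 16 before the next dose (Protocol Table 1, footnote m; Protocol 8.3.1.2).
- Formulas: SAP 16.1.2, as above.
- Extrapolation limit: AUCextra% below 20%. Profiles over it are flagged but stay in the outputs and descriptive statistics (SAP 16.1.2).
- Half-life, accumulation ratio, clearance: not given. There is no figure in the plan to reproduce.

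**Step 1, identity.** If the 24 h sample is quantifiable, AUC0-t = AUCtau on Day 15. Then

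CL/f ÷ CLss/f = (Dose/AUC0-inf) ÷ (Dose/AUCtau) = AUCtau/AUC0-inf = 1 - AUCextra.

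This follows from the SAP's own definitions and needs no PK model. On Day 15, AUCextra is itself the shortfall of CL/f against CLss/f.

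**Step 2, size for an assumed half-life.** For mono-exponential decline at steady state, AUCextra = exp(-24 λz) = 2^(-24/half-life). At 8 h, for example, 2^(-3) = 12.5%.

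**Step 3, numerical check.** Assumptions: linear one-compartment oral model, ka 1-2 per h, 15 daily doses, protocol sampling times, linear-up/log-down rule, λz from the last three points. The last two columns are relative to the true clearance.

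| Half-life (assumed) | 2^(-24/half-life) | Simulated Day 15 AUCextra | Day 15 Dose/AUC0-inf | Day 15 Dose/AUCtau |
|---|---|---|---|---|
| 4 h | 1.6% | 1.8-1.9% | 1.00-1.01 | 1.02-1.03 |
| 6 h | 6.3% | 6.7-7.1% | 0.94-0.95 | 1.01-1.02 |
| 8 h | 12.5% | 13.2-13.6% | 0.87-0.88 | 1.01 |
| 12 h | 25.0% | 25.7-26.2% | 0.74-0.75 | 1.01 |
| 18 h | 39.7% | 40.3-40.7% | 0.60 | 1.00-1.01 |
| 24 h | 50.0% | 50.5-50.8% | 0.49-0.50 | 1.00-1.01 |

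With ka 0.5-1.5 per h and exact areas, AUCtau/AUC0-inf is 0.85-0.87 at 8 h (shortfall 13-15%), 0.73-0.74 at 12 h and 0.49-0.50 at 24 h. At 4 h, small trapezoidal error offsets the shortfall of about 2%.

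**Step 4, what the limit allows.** Setting exp(-24 λz) = 0.20 gives λz = ln 5/24 = 0.067 per h, a half-life of 24 × ln 2/ln 5 = 10.3 h. A profile within the limit is therefore at most 20% low (AUC0-inf/AUCtau up to 1/0.80 = 1.25).

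**Step 5, the remedy.** With Dose/AUC0-inf on Day 1 and Dose/AUCtau on Day 15, simulated clearance is 1.00-1.03 times the true value on both days at every half-life tried (4-48 h).

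**The case against.** The strongest reply is that the list is pooled and was never meant to apply row by row to both days. CLss/f is defined for steady state, the Racc rows are ratios of the two days, and the endpoint table in SAP Section 5 says the parameters are calculated as applicable. The figures in SAP 16.1.3 name AUC0-inf only for single dose. An experienced pharmacokineticist might simply leave CL/f out on Day 15. That is fair: it makes Day 15 CL/f the literal result of the text, not a certainty. It does not supply the missing restriction, because the Day 15 tables name no parameters and the authors did write the distinction into neighbouring rows.

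A second reply is that the SAP's safeguards catch the large errors, and much of this stands. AUCextra above 20% is flagged. So is a regression window shorter than two half-lives, which any half-life of 12 h or more must fail when sampling ends at 24 h. The larger figures above therefore belong to flagged profiles. But the reliability proviso and the flags concern the terminal fit and the extrapolated share, not whether the formula suits steady state, and flagged values still enter the summaries.

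Three stronger readings are tempting and are not supported:

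- *That the bias equals the SAP's accumulation factor.* Racc(AUC) compares steady-state AUCtau with single-dose AUC0-inf and is about 1 under linear PK (0.99-1.00 in the simulation). The bias is AUC0-inf/AUCtau on Day 15.
- *That a false fall in clearance will be read as auto-inhibition.* Protocol 3.3.3 does mention time-dependent CYP3A4 inhibition by M8891. However, no Day 1 versus Day 15 comparison of CL/f is planned, and Protocol 3.3.1 predicts low perpetrator potential and only weak victim potential with strong inhibitors. The planned cross-day check of AUC is Racc(AUC), which is sound.
- *That CLss/f and Vz/f need the same restriction.* They are already tied to steady state and to single or multiple dosing.

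**Conclusion.** The point holds as a minor specification error. Followed as written, SAP 16.1.2 yields a Day 15 CL/f that understates clearance by the factor AUCtau/AUC0-inf.

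That ratio follows from the SAP's formulas, given a quantifiable 24 h sample. Its size cannot be fixed, because no half-life is stated. It runs from negligible at 4 h to about half at 24 h, and is capped at 20% for profiles within the AUCextra limit. The tabulated sizes assume linear one-compartment PK at steady state. Protocol 3.3.1 reports less than proportional exposure at 60 mg, so they are illustrations rather than predictions.

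A reader might infer that the trial's steady-state clearance will be misreported. The documents do not support that: CLss/f = Dose/AUCtau is already planned and is correct. The analysis is secondary and descriptive, and the DLT/MTD analysis does not use these parameters.

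**What to change.** In SAP 16.1.2, label AUC0-inf, AUC0-inf/Dose, AUCextra% and CL/f as Day 1 (single dose) only. State there that AUCtau and the existing CLss/f = Dose/AUCtau are the Day 15 area and clearance, and that the Day 15 tables in 16.1.3 carry these instead. The definitions of CLss/f and Vz/f and the Racc(AUC) comparison need no change for this point.

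The cost is a day label on four rows and one clarifying sentence. No new data or samples are needed, and the Day 15 output becomes slightly shorter.

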- AUC_{0-t} : Area under the concentration-time curve from time zero to the last sampling time at which the concentration is at or above the lower limit of quantification (LLOQ)
- $AUC_{0-\tau}$: Area under the plasma concentration versus time curve within one dosing interval
- $t_{1/2}$: Apparent terminal half-life
- λ_z : Apparent terminal rate constant
- CL/F : Apparent body clearance of drug following extravascular administration
- CL_{ss}/F : Apparent body clearance of drug following extravascular administration at steady state
- V_z/F : Apparent volume of distribution during the terminal phase following extravascular administration
- $Racc(AUC_\tau)$: Accumulation ratio for AUC_τ
- $Racc(C_{max})$: Accumulation ratio for C_{max} .

In dose level 4 and dose level 5, urine samples for exploratory determination of M8891 and its metabolites will be taken from the total pooled urine sample provided during the 12-hour collection period on Day 1 and Day 15. The start and stop date/time of each pooled urine collection should be recorded in the eCRF. The volume of each urine collection will also be recorded.

Additional analyses may be conducted on the plasma and/or urine samples to further investigate the presence and/or identity of drug metabolites. Any results from such analyses on plasma and/or urine may be reported separately from the clinical trial report.

Details on sample shipment and handling will be provided in the Laboratory Manual.

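### The SAP's AUC accumulation ratio divides steady-state AUCτ by single-dose AUC0-∞, so under linear PK it is 1 however much M8891 accumulates

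*SAP*

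**What the plan says.** SAP 16.1.2 gives the purpose of Racc(AUC) as "The accumulation factor to assess the increase in exposure until steady state is reached". The formula that follows is AUCτ after multiple dosing at steady state, divided by AUC0-∞ after a single dose.

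Three nearby texts bear on this:

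- Protocol 7.5.1 lists the parameter as Racc(AUCτ), with the description "Accumulation ratio for" AUCτ and no formula. The SAP's abbreviation list and its Section 5 endpoint table also name it for AUCτ.
- SAP 16.1.2 defines the companion Racc(Cmax) as Cmax on Day 15 over Cmax on Day 1.
- SAP 16.1.2 already calculates AUCτ after a single dose: it "is calculated as a partial area with the defined time range".

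The ratio is a secondary endpoint (protocol 8.3.1.2, SAP Section 5). SAP 16.1.3 reports it in the table "Individual Accumulation Ratios of AUC, Ae and Cmax in Plasma and Descriptive Statistics by Treatment".

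On dose proportionality, protocol 8.5.4.2 and SAP 16.1.4 write the same power model, y = α·dose^β, with y the PK parameter. The protocol says β should be 0 under proportionality; the SAP says 1.

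**The concern.** An accumulation ratio compares exposure over one dosing interval after repeated dosing with exposure over the same interval after the first dose. The SAP's denominator covers all time, including the exposure that carries over beyond 24 h and produces the accumulation. Dividing by it cancels the effect the ratio is meant to show.

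If M8891 accumulates and its kinetics are roughly linear, the accumulation table would show an AUC ratio near 1 beside a Cmax ratio well above 1. A reader could take the AUC row to mean no accumulation. The concept has a use in this trial: protocol 7.4.5.1 lets the SMC waive the Day 15/16 ECGs if no relevant accumulation is seen. Nothing shows that the SMC relies on this ratio, and SAP Section 4 places SMC analyses in a separate plan.

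The denominator is also fragile. The Day 1 profile ends at 24 h (protocol Table 1, footnote m), so for a longer half-life much of AUC0-∞ is extrapolated.

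**Working it through.** The plan states no accumulation value to reproduce, so the check is of the formula.

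**1. From the SAP's own definitions.** SAP 16.1.2 sets CL/f = Dose/AUC0-∞ and CLss/f = Dose/AUCτ. At a constant dose,

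Racc(AUC) = AUCτ(steady state) / AUC0-∞(single dose) = (CL/f) / (CLss/f).

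This is the ratio of two clearances, which is 1 if clearance does not change.

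**2. By superposition.** With linear, time-invariant kinetics and daily dosing (τ = 24 h), the Day 15 interval holds the contributions of 15 doses. Its area equals the single-dose area from 0 to 15 × 24 = 360 h. Hence

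- SAP ratio = AUC0-360 / AUC0-∞, close to 1 once steady state is near;
- Day 15/Day 1 ratio of AUCτ = AUC0-360 / AUC0-24, which rises with half-life.

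**3. Numbers.** Inputs from the documents: τ = 24 h, Day 15, last Day 1 sample at 24 h. Assumptions: one compartment, first-order absorption with ka = 1/h, and the half-lives shown. For unit dose over volume, with k = ln 2/t½,

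C(t) = ka/(ka − k) × (e^(−kt) − e^(−ka·t)), so AUC0-∞ = 1/k.

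Example, t½ = 24 h: AUC0-∞ = 34.625, AUC0-360 = 34.624, AUC0-24 = 16.797.

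- SAP ratio: 34.624/34.625 = 1.00
- Day 15/Day 1 AUCτ: 34.624/16.797 = 2.06
- Extrapolated share on Day 1: 1 − 16.797/34.625 = 51.5%

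| Assumed t½ (h) | SAP Racc(AUC) | AUCτ Day 15/Day 1 | Racc(Cmax) | Day 1 AUC extrapolated |
|---|---|---|---|---|
| 6 | 1.00 | 1.08 | 1.08 | 7.1% |
| 12 | 1.00 | 1.36 | 1.36 | 26.5% |
| 24 | 1.00 | 2.06 | 2.04 | 51.5% |
| 48 | 0.99 | 3.52 | 3.46 | 71.7% |

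For ka from 0.5 to 2/h, the AUCτ ratio ranges over 1.07–1.09, 1.35–1.39, 2.03–2.13 and 3.46–3.66. The SAP ratio falls visibly below 1 only when Day 15 is short of steady state (0.925 at t½ = 96 h).

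**4. With the planned estimator.** The linear-up/log-down rule at the Part 1 sampling times (0, 1, 2, 3, 4, 5, 6, 8, 12, 24 h), without noise and with ka = 1/h, gives AUCτ Day 15/Day 1 of 1.08, 1.36, 2.07 and 3.53. The SAP ratio is 1.00, 1.00, 1.00 and 0.99.

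**5. Reliability of the denominator.** The extrapolated share passes the SAP's 20% limit at a half-life of 9.4, 9.9 and 10.1 h for ka = 0.5, 1 and 2/h. The SAP also asks that "the observation period over which the regression line is estimated should be at least twofold the resulting" half-life. A 24 h profile cannot meet this for a half-life of 12 h or more, because 2 × 12 = 24 h and the concentration at tmax is excluded from the regression.

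**6. Dose-proportionality slope.** Exactly proportional data at 7 to 210 mg, fitted as log(y) on log(dose), give β = 1 for y as written and β = 0 for y divided by dose.

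**The case against.** The algebra needs linear, time-invariant kinetics, and the documents do not establish that. Protocol 3.3.1 reports less than proportional exposure at 60 mg, and 3.3.3 describes time-dependent inhibition of CYP3A4 by M8891. This stands as a condition on the value 1. It does not rescue the formula: if clearance changes over time, the SAP ratio measures that change, which is still not accumulation.

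The large contrasts arise where the denominator would already be flagged. Near steady state the AUCτ ratio is about 1/(1 − extrapolated share), so below the 20% limit it is at most 1/(1 − 0.20) = 1.25. The flagging of Racc(AUC) itself is less clear. The 20% rule has a closed list that does not name it. The regression-window rule covers derived parameters in open-ended terms and may reach it. In either case the values "will be included in the parameter outputs and descriptive statistics but will be flagged and discussed appropriately", so they stay in the summary, and a flag does not make the ratio measure accumulation.

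Accumulation is visible elsewhere: in Racc(Cmax), in AUCτ by day, in the table "Individual Trough Plasma Concentrations of M8891 and Descriptive Statistics by Scheduled Time and Dose Group" and in the single- and multiple-dose overlay plots. All analyses are descriptive. This stands and limits the harm to a misleading row for a named secondary endpoint.

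A text-extraction error in the formula is possible, but τ and ∞ are rendered distinctly within that same formula.

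On the slope, the protocol's preceding sentences concern dose-normalised parameters, for which 0 is right, and the protocol defers detail to the analysis plan. That makes it a wording matter.

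**Conclusion.** The concern holds. As defined, Racc(AUC) does not do what the SAP says it does: under linear, time-invariant kinetics it is 1 at every half-life. The protocol's name for the parameter, the Day 15/Day 1 form of Racc(Cmax) and the availability of single-dose AUCτ all suggest a slip in the denominator.

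How much it matters for M8891 depends on a half-life the documents do not give. At 6 h the row would read 1.00 in place of 1.08, which is negligible. At 12 h it would read 1.00 in place of 1.36, and at 24 h 1.00 in place of 2.06, beside a Cmax ratio of 2.04. These figures assume one compartment and ka = 1/h.

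The formula should be corrected before the analysis is run, but no conclusion about safety or dose in these documents rests on it. The slope contradiction is minor: the SAP already uses 1, and no decision rule is attached.

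**What to change.** In SAP 16.1.2, define Racc(AUC) as AUCτ on Day 15 divided by AUCτ on Day 1. This matches Racc(Cmax) and the protocol's name for the endpoint.

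If the present ratio is kept as well, label it a time-linearity ratio and add it to the parameters flagged when the extrapolated share of AUC exceeds 20%.

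In protocol 8.5.4.2, change the reference slope to 1, or state that 0 applies only to the dose-normalised model.

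The cost is one formula line in the SAP and one sentence in the protocol. No new samples or data are needed.
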